9.4 Statistical Analysis for Adverse Events and Toxicity Measures

The frequencies of adverse events (AEs) and toxicity measures (e.g., CBC, liver function test, body weight) will be compared between the SF treatment and placebo arm. The analysis will be conducted for total AEs and specific AEs, expected AEs and unexpected AEs, AEs by grade and attribution grouping, respectively, at each clinical visit as well as the summed total over 4 time points of the entire treatment period. We will repeat the same analysis on a patient level. Chi-square test will be used for comparing the frequencies between the two treatment groups.

Sample Size Consideration. As described in Table 3 above, the frequencies of AEs reported were low in previous studies. Based on the frequencies reported by Atwell et al, the frequency of total AE in placebo was 33% (9 out of 27 participants), the proposed study with a total of 72 subjects will have an 80% statistical power to detect a doubled frequency (67%) of total AEs in the SF-treatment group. The proposed study can detect a less excess AE rate between the two treatment groups if all AEs over different time points are combined or all AEs are counted independently.

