(DTC). Two of 12 individuals (both receiving active preparations) showed an increase in plasma ALT exceeding the upper limit of normal with one meeting criteria for a Grade 1 toxicity. Notably, ALT levels rose for all subjects during the course of the study including placebo-treated subjects. Plasma AST levels rose above normal on Day 19 for 2 of 12 subjects. They were released from the inpatient portion of the study on Day 17 and their post-discharge activities (i.e., possible alcohol intake) could not be ascertained. Monitoring of TSH levels demonstrated that in 3 of 12 subjects (2 active treatment, 1 placebo), TSH levels exceeded the upper limit of normal during or after the dosing period. Notably, TSH levels rose for 11 of 12 subjects during the first 6 Days of hospitalization before broccoli seed administration was begun. TSH increases were not associated with any clinical symptoms or abnormalities of T3 or T4. Evaluation by 2 independent endocrinologists determined that the changes in TSH were mild and reversible and did not pose an obstacle to further studies with administration of BSPs. No other significant laboratory abnormalities occurred. Thus, this Phase I safety study in healthy volunteers revealed no evidence of systematic, clinically significant adverse effects that could be attributed to the administration of repeated doses of broccoli sprout extracts containing SF or GR (31).

Cornblatt *et al.* (29) conducted a study to assess the bioavailability of SF-rich broccoli sprout extract in human breast tissue. In this proof-of-principle study, 8 women undergoing elective mammoplasty consumed a preparation containing 200 μ mol of SF approximately 50 minutes prior to surgery. The extract was well-tolerated without any adverse events or complications. SF metabolite levels measured by cyclocondensation reaction as dithiocarbamates were used to determine SF distribution. Mean post-dose plasma dithiocarbamate (DTC) level was 0.92 ± 0.72 μ M, and mean epithelial/stromal enriched breast tissue DTC concentration was 1.45 ± 1.12 and 2.00 ± 1.95 picomol/mg tissue for right and left breast respectively. In addition, the investigators were able to measure NQO1 and HO-1 transcripts in the human breast tissue, demonstrating the feasibility of assessing a 24harmacodynamics action of SF in these tissues (29).

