5. TREATMENT PLAN AND STUDY PROCEDURES

5.1 Pre-Treatment Evaluation

Pretreatment tests should be performed within 90 days prior to the randomization.

- 1) Signed informed consent
- 2) Questionnaire data collection on patient's characteristics and smoking history.
- 3) Physical exam including height, weight, vitals and SWOG performance status.
- 4) FEV1/FVC
- 5) Blood oxygen saturation
- 6) Expired Carbon Monoxide
- 7) Laboratory analysis including CBC and serum chemistries such as total bilirubin, AST, ALT, BUN, creatinine, .
- 8) Baseline bronchoscopy: Prior to randomization, all participants will undergo a bronchoscopy at the Endoscopy Suite at the UPMC Shadyside Hospital. The procedure will be carried out by [name] (Co-PI) using Narrow Band Imaging (NBI) white-light bronchoscopy. The patient's nose, throat, vocal cords and windpipe are sprayed with Lidocaine (numbing medicine) to help keep patient from coughing and to numb patient's airways. During the procedure, [name] will perform a complete airway examination including visualization of the vocal cords, trachea, main carina, and orifices of the sub-segmental bronchi to the extent that it is visible without causing trauma to the bronchial wall. Biopsy samples will be collected at the pre-determined sites. Some of these biopsies will be used for the pathological examination. Any patients with lung cancer or carcinoma in situ will be ineligible for the present study. We will inform subjects the abnormal biopsy results and provide appropriate counseling from qualified medical personnel.

Since the clinical significance of moderate or severe dysplasia is unknown and no effective treatment available, we will not conduct additional clinical procedure or intervention on these patients beyond routine follow-up and care. The patients with dysplasia will be monitored at each clinical visit (once every three months during the treatment period) according to the study protocol. At the end of study period, another biopsy at the same site of initial locations that show dysplasia will be performed to evaluate the change (progress, regress or no change) of these lesions detected at baseline biopsy. This is one of the primary outcome measures for the proposed study. After the completion of the study, the patients will continue to receive routine medical care including annual CT screening if eligible.

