5.5 Clinical Visits

Besides two clinical visits in stage 1 of the study for eligibility screening, all eligibility study participants will begin taking the study tablets at visit 1 of stage 2 of the study and return to the study clinic at the end of months 3, 6, 9, and 12 (the end of treatment period). At each clinical visit, the clinical research nurse/assistant will conduct the following:

- 1) Exam the subject's diary for dosing and timing of intake of test tablets, and keep the diary in subject's folder.
- 2) Count and record the remaining tablets given.
- 3) Provide new study tablets that will supply the next 3 months.
- 4) Study participant will turn in the self-administered questionnaire for recording his/her intake of cruciferous vegetables in the past 3 months using a dietary frequency questionnaire (Appendix 5).
- 5) Collect blood, spot urine and nasal brushing samples
- 6) Conduct pulmonary function test: FEV1/FVC
- 7) Collect safety and toxicity measures at each clinical visit (once every 3 months) during the 12-month treatment period:
 - a) Collect adverse events (AEs) using the AE Recording Form (Appendix 8)

- b) Conduct physical examination including body weigh, height, and vitals by a registered nurse and record the results in the patient's study file
- c) Laboratory evaluation: CBC with platelets and differential, chemistry panel including liver function testing.
- 8) Only at the end of treatment period, bronchoscopy will be performed on the patient using the same procedure as described above in 5.1(8) and bronchial biopsies and lavage samples collected (stage 2- visit 5).

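### Section 9.4 names only a chi-square test on frequencies for laboratory values and body weight, sets no cut-offs and plans no baseline-adjusted analysis, which can lose much of the power to see a moderate mean shift.

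*Combined protocol and SAP*

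**What the plan says.** Section 9.4 opens with one sentence for both kinds of safety data: the frequencies of adverse events and "toxicity measures (e.g., CBC, liver function test, body weight) will be compared between the SF treatment and placebo arm". The breakdowns that follow (total, specific, expected, unexpected, by grade, by attribution) are all of adverse events, and are made "at each clinical visit as well as the summed total over 4 time points of the entire treatment period". It adds: "We will repeat the same analysis on a patient level". The only test is in the last sentence of that paragraph: "Chi-square test will be used for comparing the frequencies between the two treatment groups".

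The data are richer than that. Section 5.1 requires, before randomization, "Laboratory analysis including CBC and serum chemistries such as total bilirubin, AST, ALT, BUN, creatinine", and body weight at the physical examination. Section 5.5 then says: "Collect safety and toxicity measures at each clinical visit (once every 3 months) during the 12-month treatment period". Its list includes body weight and "Laboratory evaluation: CBC with platelets and differential, chemistry panel including liver function testing".

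Sections 9.1 and 9.2 treat other measures taken before and after treatment differently. Average and worst histology scores, Ki-67, caspase-3 and TUNEL are analysed by linear regression on treatment, controlling for the pre-treatment value. Section 9.1 calls this ANCOVA approach optimally efficient for such a design.

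**The concern.** Laboratory values and weight are continuous. A chi-square test can be applied to them only after each is cut into categories, and Section 9.4 does not say where to cut or whether the cut refers to the baseline. CTCAE 4.0 is named in Section 7.1 for grading adverse events, but Section 9.4 does not tie the laboratory comparison to it. No section plans a change-from-baseline summary, a regression, a mixed model or a confidence interval for these measures.

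Two things are at stake. First, a fixed limit that few patients cross responds weakly to a moderate shift of the whole distribution, so a between-arm difference in, say, ALT could go unseen with 36 patients per arm. Second, a cut-off chosen after the data are seen leaves the safety result open to choice. Eligibility criterion 6 also admits patients with AST or ALT up to 2.5 times, and bilirubin up to 1.5 times, the upper limit of normal. A plain count above that limit would therefore mix abnormality present at entry with change on treatment. Safety and toxicity over 12 months is a stated secondary aim.

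**Working it through.** **The plan's own figure.** Section 9.4 states 80% power to detect 33% against 67% total adverse events with 72 subjects. Enumerating two binomials with 36 per arm and rates 1/3 and 2/3, the uncorrected Pearson chi-square at two-sided 0.05 has 81.2% power, so the figure reproduces. With the 60 completers of Section 9.1 (30 per arm) it is 75.6%. This covers total adverse events only; the documents give no power for laboratory values or weight.

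**Inputs from the documents.** 36 per arm randomized; 30 per arm completing; one baseline and four on-treatment visits. Two-sided 0.05 is stated in Section 9.1 and assumed for 9.4.

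**Assumptions not in the documents.** A shift s = 0.5 SD at every on-treatment visit; normal values (log scale where needed); a fixed limit c exceeded by 2.5%, 5% or 10% of placebo values at one visit; equal correlation r = 0.5 to 0.7 between any two visits of the same person.

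**Chi-square at one visit.** The SF exceedance is 1 − Φ(c − 0.5).
- 2.5% placebo gives 7.2% SF; 5% gives 12.6%; 10% gives 21.7%.
- Exact power: 12%, 22% and 28% with 36 per arm; 9%, 18% and 24% with 30.

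**Chi-square on any of four visits, per patient.** The probability of at least one exceedance is 1 − ∫ φ(u) Φ[(c − s − u√r)/√(1 − r)]⁴ du, with s = 0 for placebo. At the 5% limit, r = 0.5 gives 14.4% against 31.2%, and r = 0.7 gives 12.0% against 26.3%.

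| Per-visit placebo rate | Power, 36 per arm (r = 0.5 / 0.7) | Power, 30 per arm (r = 0.5 / 0.7) |
|---|---|---|
| 2.5% | 33% / 28% | 28% / 24% |
| 5% | 40% / 34% | 34% / 29% |
| 10% | 48% / 42% | 40% / 35% |

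**Baseline-adjusted regression.** For the mean of k visits, the residual variance is v = (1 + (k − 1)r)/k − r², the standard error is √(2v/n), and power is about Φ(0.5/SE − 1.96).

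| k | r | v | SE, n = 36 | Power, n = 36 | Power, n = 30 |
|---|---|---|---|---|---|
| 1 | 0.5 | 0.750 | 0.204 | 69% | 61% |
| 1 | 0.7 | 0.510 | 0.168 | 84% | 77% |
| 4 | 0.5 | 0.375 | 0.144 | 93% | 89% |
| 4 | 0.7 | 0.285 | 0.126 | 98% | 95% |

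A simulation of 10,000 trials with the t-test version of ANCOVA and 36 per arm agrees: 67% and 83% for one visit, 92.5% and 97.6% for the mean of four.

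**Sensitivity to the category definition.** Suppose the category is a rise from baseline, with the limit set so that 2.5-10% of placebo patients exceed it at one visit. Then c is replaced by c√(2(1 − r)) on the change scale. With 36 per arm, the any-visit chi-square has 33-48% power at r = 0.5 (the same as for fixed limits), about 51-69% at r = 0.7, and about 71-85% at r = 0.8. Regression over four visits at r = 0.8 has 99.6% (v = 0.210, SE = 0.108).

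**The case against.** The strongest reply is that frequencies of graded abnormalities are a normal safety display, that the monitoring board reviews frequency and grade by arm (Section 7.4), and that safety is a secondary aim whose sample size rests on total adverse events. That stands: the tables should stay. The gap is that they are the only analysis.

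A second reply is that the sentence is ambiguous. The chi-square may be meant for adverse events alone. That is a fair reading, but it leaves the laboratory values and weight with no method, so the remedy is the same.

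Several stronger readings are tempting, and the documents do not support them.
- A reader might infer that the plan always discards most of the power. It gives no cut-off and does not rule out change-from-baseline categories, for which the loss can be modest.
- A reader might infer that the repeated values are ignored. Section 9.4 analyses each visit, the sum over four time points and the patient level, so they are used, though crudely. It would therefore be unfair to set a one-visit chi-square (22% at the 5% limit) against a four-visit model (93-98%).
- Section 4.1.6.2 reports of the phase I study that "ALT levels rose for all subjects during the course of the study including placebo-treated subjects". This does not by itself call for baseline adjustment, because a rise common to both arms cancels in a randomized comparison. In the larger 84-dose trial in the same section, the means of 13 analytes were identical between arms.
- A reader might infer that all other endpoints use baseline-adjusted linear models. The dysplasia index uses a binomial GEE with a common baseline, and the nasal-bronchial model in Section 9.3 has no baseline term.
- Nothing says that a non-significant chi-square would be reported as no difference, and no section shows that a 0.5 SD shift matters clinically.

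**Conclusion.** The concern holds as a gap in the analysis plan with a better method at hand. On either reading of Section 9.4, continuous safety measures with a baseline and repeated values have no baseline-adjusted comparison and no defined categories.

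The size is conditional on the assumptions listed in the check. Comparing like with like under fixed limits and 36 per arm, power is roughly 12-28% against 69-84% at one visit, and 28-48% against 93-98% over four visits. With 30 completers per arm the figures are about 9-24% against 61-77%, and 24-40% against 89-95%. The direction does not change across the ranges examined, but the size does: change-from-baseline categories with correlation 0.8 bring the four-visit loss down to about 71-85% against 99.6%. The supportable statement is that the plan can lose much of the power, depending on a definition that it does not give.

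**What to change.** In Section 9.4:
1. State that the chi-square comparison applies to adverse events and to categorised laboratory and weight results. Give the cut-offs and say whether they refer to the baseline value.
2. Keep the frequency or shift tables of abnormal or graded values as a descriptive safety display.
3. For each continuous safety measure (log scale for ALT, AST and bilirubin), add a mixed model or ANCOVA over the scheduled on-treatment visits, adjusted for the pre-randomization value. Report the SF-placebo difference with a 95% confidence interval.
4. Say that these are estimates with intervals and not confirmatory tests, since there will be several analytes.

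The cost is a few lines of text and code, with no new data or visits. The small downside is more analysis work and a longer set of per-analyte estimates, which point 4 addresses. The cut-offs and models should be fixed before unblinding.

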1.2 Secondary Aims

- 1.2.1 To explore if daily oral dose of 120 micromole SF for 12 months can modulate the changes of the lung cancer-related gene expression markers in bronchial epithelia in former smokers at high risk for lung cancer.
- 1.2.2 To explore if daily oral dose of 120 micromole SF for 12 months can modulate the changes of bronchial premalignant lesions-related gene expression markers in former smokers at high risk for lung cancer.
- 1.2.3 To explore if daily oral dose of 120 micromole SF for 12 months can modulate the similar changes of the gene expression markers in nasal epithelia as in the bronchial epithelia identified in Aims 1.2.1 and 1.2.2.

- 1.1.4 To determine the safety and toxicity of daily oral dose of 120 micromole SF for 12 months in former smokers at high risk for lung cancer.

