9. STATISTICAL AND SAMPLE SIZE CONSIDERATIONS

This is a randomized, double blind, placebo-controlled study to evaluate the efficacy of SF as a chemopreventive agent. Eligible subjects are former smokers with ≥ 30 pack-years smoking history who quit smoking < 15 years, and are considered at high risk for developing lung cancer. The proposed duration of therapy will be 12 months for each subject. The primary objective of this trial is to assess whether oral SF supplementation elicits an increased histologic response when compared to placebo in this population over a 12-month treatment period. The planned sample size is 72 subjects (36 per treatment arm). A block randomization scheme will be used to ensure that both treatment and placebo group have the same proportion of men and women, respectively. The randomization will be done at the UPMC Hillman Cancer Center.

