Sample size consideration. In the iloprost trial, 57 former smokers were randomized to receive oral iloprost or placebo for 6 months. Treatment effects (adjusted for baseline levels) were statistically significant ($P \leq 0.01$) for all 3 endpoints (dysplasia index, average dysplasia score, worst dysplasia score). Anticipating a 20% dropout rate over 12 months, we will randomize at least 72 study subjects to ensure that 60 subjects complete our SF study. Assuming an average baseline dysplasia index of 22% and post-therapy 11% for subjects receiving SF, a simulation with 10,000 trials with a sample size of 60 subjects has yielded an 80% statistical power to detect a statistically significant (two-sided $p < 0.05$) treatment effect, using generalized linear models (binomial family, 6 biopsies) after controlling for baseline levels of DI. Calculations are similar for other endpoints, and actual power should be greater than the DI measure because they are continuous measures and have observed within-subject correlation (i.e., repeated measures).

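### Section 9.4 answers the safety aim with chi-square tests alone; at 36 per arm a non-significant result cannot support a conclusion of no excess toxicity, and no estimate, interval or upper bound is pre-specified

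*Combined protocol and SAP*

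**What the plan says.** Section 1.2 lists among the secondary aims (in an item numbered 1.1.4): "To determine the safety and toxicity of daily oral dose of 120 micromole SF for 12 months".

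Section 9.4 is the analysis for that aim. It compares AE and toxicity frequencies between arms for total and specific AEs, expected and unexpected AEs, and by grade and attribution, at each visit and summed over four time points, then repeats the analysis per patient. The one method named is: "Chi-square test will be used for comparing the frequencies between the two treatment groups".

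The sample-size paragraph takes its base rate from an earlier breast-biopsy trial, where "the frequency of total AE in placebo was 33% (9 out of 27 participants"), and claims "80% statistical power to detect a doubled frequency (67%) of total AEs in the SF-treatment group" with 72 subjects. It adds that a smaller excess can be detected by pooling AEs over time points or treating every AE as a separate count. Section 9 gives the size: "The planned sample size is 72 subjects (36 per treatment arm").

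Sections 7.4 (safety board review by arm) and 8.3.4 (safety assessment) add no estimate, margin or bound.

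**The concern.** A test asks whether the data are incompatible with no difference. Determining safety also needs a statement of how large an excess remains compatible with the data. With 36 per arm those are far apart, and the plan commits only to the first. The power statement covers a single case, a 34-point rise in total AEs, and gives nothing for any specific AE.

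This matters because the trial is meant to support SF's further development for primary prevention. Section 2.2 describes SF as having minimal side effects, and section 4.2 expects that participants can go on taking the supplement afterwards. The studies in Table 3 lasted 84 days at most, and the longest human exposure described in section 4.1.6.2 is 20 weeks. Twelve months of placebo-controlled AE data would therefore be new information, and a p-value conveys little of it.

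**Working it through.** **Inputs.** 36 per arm (section 9). Placebo rate of any AE 9/27 = 33% (section 9.4). Placebo rates in Table 3: bloating 5/27 = 18.5%, gas/flatulence 4/27 = 14.8%, diarrhea 2/27 = 7.4%. Alpha is not stated in 9.4; I assume the level used for the dysplasia index in 9.1, "statistically significant (two-sided $p < 0.05$) treatment effect". The 50% rate and the doublings of specific AEs are my choices, since the documents define no relevant excess.

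**Step 1: reproduce the plan's figure.** Per arm, n = [1.96√(2p̄(1-p̄)) + 0.8416√(p₁(1-p₁) + p₂(1-p₂))]² / (p₂-p₁)². For 1/3 against 2/3, with p̄ = 1/2: (1.96 × 0.7071 + 0.8416 × 0.6667)² / (1/9) = 34.1, so 35 per arm or 70 in total, against 72 planned. Power at 36 per arm is 82% by this approximation and 81% by exact enumeration of the uncorrected chi-square. The stated 80% holds.

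**Step 2: power for smaller excesses.** Power = Φ{[(p₂-p₁)√n - 1.96√(2p̄(1-p̄))] / √(p₁(1-p₁) + p₂(1-p₂))}. For 1/3 against 1/2: (0.1667 × 6 - 1.96 × 0.6972) / 0.6872 = -0.53, and Φ(-0.53) = 0.30. The same formula and the exact enumeration give:

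| Placebo to SF | Approximate | Exact |
|---|---|---|
| Any AE, 33.3% to 66.7% | 82% | 81% |
| Any AE, 33.3% to 50% | 30% | 29% |
| Bloating, 18.5% to 37.0% | 41.7% | 42.5% |
| Flatulence, 14.8% to 29.6% | 32% | 32% |
| Diarrhea, 7.4% to 14.8% | 17% | 18% |

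Solving for 80% power from a 33.3% base gives about 66%, a rise of about 33 points. If AE data were available only for the 30 completers per arm expected in 9.1, power for 33.3% to 50% would be about 26%.

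**Step 3: what a non-significant result leaves open.** Take 18/36 on SF and 12/36 on placebo. Pooled rate 30/72 = 0.4167; SE = √(0.4167 × 0.5833 × 2/36) = 0.1162; z = 0.1667/0.1162 = 1.43; p = 0.15. The Wilson limits are 0.345 to 0.655 and 0.202 to 0.497. The Newcombe interval is then:
- lower: 0.1667 - √(0.1553² + 0.1633²) = -0.059
- upper: 0.1667 + √(0.1553² + 0.1312²) = +0.370

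So the interval runs from -6 to +37 points. With 12/36 in both arms it is still ±21 points.

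**Step 4: events not seen.** With 0/36 on SF, the exact one-sided 95% upper bound is 1 - 0.05^(1/36) = 8.0%.

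**Step 5: pooling over visits.** Four visits give 36 × 4 = 144 patient-visits per arm. With within-patient correlation ρ, the effective number is 144 / (1 + 3ρ), from 144 if ρ = 0 down to 36 if ρ = 1. The documents give no ρ. Counting repeat events as independent assumes the top of that range.

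**Step 6: validity for uncommon events.** At 7.4% the expected count is 36 × 2/27 = 2.7 per arm, below the usual minimum of 5 for the chi-square approximation. Section 9.4 names no exact test. With Fisher's exact test, power for the diarrhea doubling is 8%.

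**The case against.** A reader might infer that the plan treats p > 0.05 as proof of safety. It does not: no section sets a rule for concluding safety. AE frequencies by arm will be compared and the safety board will review them, so the counts will exist and an interval could be worked out from them. What is missing is the commitment to an estimate and interval.

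A reader might also infer that the trial would probably miss any excess of 10 to 17 points altogether. The figures above are for single tests. Section 9.4 plans many, across types, grades, attributions and visits, and the chance that at least one falls below 0.05 is higher than any one of them suggests. That is not a sound basis for a safety conclusion either, but it rules out predicting a uniformly non-significant report.

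The power limit is disclosed for total AEs, and the arithmetic is right. Safety is a secondary aim in a phase 2 trial sized on histology, and low power for AEs comes with 72 subjects. All of this stands, and it limits the weight of the point. It does not remove it: a small sample is the reason to report intervals.

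The remark that a smaller excess becomes detectable by pooling or separate counting does not help. Events in the same patient are correlated, so the gain is overstated unless the correlation is modelled. Pooling into whether a patient ever had an AE adds no subjects; it is the patient-level test already computed above.

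**Conclusion.** The point holds as a gap in what the analysis can answer; the sample-size arithmetic is not at fault. As written, 9.4 can detect with 80% power only about a doubling of total AEs, from 33% to about 66%. A rise to 50%, or a doubling of bloating, flatulence or diarrhea from its Table 3 placebo rate, would be missed more often than found (power about 30%, 42%, 32% and 18%). A non-significant test therefore cannot by itself support a statement of no excess toxicity.

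This rests on a two-sided 5% level, 36 evaluable patients per arm, the uncorrected chi-square, and placebo rates from a study lasting 2 to 8 weeks. Rates over 12 months may differ. No primary conclusion is affected, and this is a cheap improvement.

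**What to change.** In section 9.4:

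- Make the patient-level risk difference (SF minus placebo) with a 95% confidence interval, for example Newcombe's, the main safety summary for any AE, any grade ≥2 AE and each specific AE.
- Where no event of a type is seen on SF, give the exact one-sided 95% upper bound on the rate (8.0% for 0/36).
- Keep the chi-square test as descriptive, with Fisher's exact test when expected counts are below 5, and state the significance level.
- Delete the sentence about counting AEs separately, or qualify it by saying that repeat events in one patient are correlated.
- State that p > 0.05 is not evidence of no excess risk and that safety wording will refer to the upper limit of the interval.

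The cost is some SAP text and one more column in the AE tables, with no new patients or data. The safety statement will look less favourable, because the intervals will be wide. The fix does not raise power and sets no margin; it shows how large an excess the data leave open.
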